The primary endpoint will additionally be analyzed using a discrete-time Cox proportional hazards (CPH) time to event statistical model, if the hazards by treatment group can be assumed

proportional using a graphical comparison of log-minus-log survival curves and no more than two-thirds of the recovery times are censored in each treatment group. The CPH model will be used for descriptive purposes, with treatment group, age group and injection site modeled as categorical effects, and baseline plasma glucose modelled as a continuous covariate. The treatment group hazard ratios of active versus placebo, will be estimated together with the 95% confidence intervals, and pairwise treatment group inferences (dasiglucagon vs placebo, GlucaGen vs placebo, dasiglucagon vs GlucaGen) will be evaluated using least-square mean and standard deviation estimates.

Due to the discrete nature of blood sampling in time, and the fact that there must be a true, but unmeasured, ordering of the recovery times, the method using the “exact discrete” partial likelihood for tied failure times will be applied. In SAS, this is implemented in the `phreg` procedure with the option `ties=discrete`. The influence of age and injection site on time to recovery will also be evaluated in the proportional hazards model by a ‘type 3’ test in the `phreg` procedure.

In addition, separate CPH models will be calculated to evaluate homogeneity for the following factors:

Sex, BMI class, ethnicity, race, US/non-US.

These additional homogeneity models are only presented for the primary efficacy analysis, but not for subsequent variants of that analysis.

To obtain an estimate of these true, but unassessed, patient recovery times, a linear interpolation (between the two time points before and after recovery is observed) will be carried out to estimate the patients’ actual time of recovery. These derived recovery times will be described and analysed in the same manner as for the discrete times above.

Let  $t_1$  and  $t_2$  be the 2 time points before and after recovery is observed and  $y_1$  and  $y_2$  be the corresponding changes from baseline in glucose concentrations, where  $y_1$  is below 20 mg/dL and  $y_2$  is greater than 20 mg/dL.

The interpolated time point  $t_{ext}$  is calculated then as:

$$t_{ext} = t_1 + \frac{(20 - y_1) * (t_2 - t_1)}{(y_2 - y_1)}$$

This linear interpolation is only used as a supportive analysis to the primary analysis model using `proc lifetest`.

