In this statistical model, `ties=exact` will be used.

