PT Term 1	xx ( xx.x) xx	xx ( xx.x) xx	xx ( xx.x) xx	xx ( xx.x) xx
PT Name 2	xx ( xx.x) xx	xx ( xx.x) xx	xx ( xx.x) xx	xx ( xx.x) xx
PT Name 3	xx ( xx.x) xx	xx ( xx.x) xx	xx ( xx.x) xx	xx ( xx.x) xx
PT Name xx	xx ( xx.x) xx	xx ( xx.x) xx	xx ( xx.x) xx	xx ( xx.x) xx
ATC class xx				
PT Name 1	xx ( xx.x) xx	xx ( xx.x) xx	xx ( xx.x) xx	xx ( xx.x) xx
PT Name 2	xx ( xx.x) xx	xx ( xx.x) xx	xx ( xx.x) xx	xx ( xx.x) xx
PT Name 3	xx ( xx.x) xx	xx ( xx.x) xx	xx ( xx.x) xx	xx ( xx.x) xx
PT Name xx	xx ( xx.x) xx	xx ( xx.x) xx	xx ( xx.x) xx	xx ( xx.x) xx
...				

Note: At each level of summation (overall, ATC class, preferred name) patients reporting more than 1 medication/ treatment are counted only once.  
Table is sorted by descending total patient count  
Percentages are based on total no. of subjects in each treatment group

PROGRAM SOURCE:###, DATA CUT OFF DATE: ddmmyyyy

RUN DATE: ddmmyyy hh:mm CET

14.2.1.1: Time to plasma glucose recovery - summary table, FAS

Primary model

	Treatment			p-values
	dasiglucagon (N=xxx)	GlucaGen (N=xx)	placebo (N=xx)	
Status (N)	Xx	xx	xx	
Recovered 	xx (xx.xx)	xx (xx.xx)	xx (xx.xx)	
Censored 	xx (xx.xx)	xx (xx.xx)	xx (xx.xx)	
Time to recovery (minutes)				
25th percentile	xx.x	xx.x	xx.x	
Median (95% CI)	xx.x (xx.x ; xx.x)	xx.x (xx.x ; xx.x)	xx.x (xx.x ; xx.x)	
75th percentile	xx.x	xx.x	xx.x	
Dasiglucagon versus Placebo P-value (log-rank test - stratified)				x.xxxx
P-value (log-rank test - non-stratified)				x.xxxx
P-value (Wilcoxon test) - stratified				x.xxxx
Dasiglucagon versus GlucaGen				
P-value (log-rank test - stratified)				x.xxxx
P-value (log-rank test - non-stratified)				x.xxxx
Cox proportional hazards 				
Hazard ratio	xx.xx	xx.xx	1	
95% profile CL	(xx.xxx ; xx.xxx)	(xx.xxx ; xx.xxx)		
P-values				
Dasiglucagon versus Placebo				x.xxxx
Dasiglucagon versus Glucagen				x.xxxx
Glucagen versus Placebo				x.xxxx
Type 3 test for Age				x.xxxx
Type 3 test for injection site				x.xxxx

1: Increase of plasma glucose of 20 mg/dL within 45 min without iv glucose

2: Did not recover within 45 min or received iv glucose before 45 min

3: Cox proportional hazard model with treatment, age and injection site as fixed effects and baseline plasma glucose as covariate

[figure not shown]
Homogeneity models

	Treatment		
	dasiglucagon (N=xxx)	GlucaGen (N=xx)	placebo (N=xx)
Cox proportional hazards 			
			
Hazard ratio	xx.xx	xx.xx	1

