95% profile CL	(xx.xxx ; xx.xxx)	(xx.xxx ; xx.xxx)	
			
Hazard ratio	xx.xx	xx.xx	1
95% profile CL	(xx.xxx ; xx.xxx)	(xx.xxx ; xx.xxx)	
.. .			
			
Hazard ratio	xx.xx	xx.xx	1
95% profile CL	(xx.xxx ; xx.xxx)	(xx.xxx ; xx.xxx)	

1: Cox proportional hazard model with treatment, age and injection site as fixed effects and baseline plasma glucose as covariate

14.2.1.2: Time to plasma glucose recovery - Kaplan Meier survival curve, FAS

*Note: this is a generic example using example data from SAS Institute; number of patients at risk are adapted to 0, 10, 15, 20, 30 and 45min.*

PROGRAM SOURCE:###, DATA CUT OFF DATE: ddmmyyyy

RUN DATE: ddmmyy hh:mm CET

14.2.1.3: Time to plasma glucose recovery - summary table, PP

→ Repetition of table 14.2.1.1 with different selection of population. Only page 1 output presented here.

14.2.1.4: Time to plasma glucose recovery - Kaplan Meier survival curve, PP

→ Repetition of table 14.2.1.2 with different selection of population.

Zealand Pharma A/S  
ZP4207-17086 (ZEA-DNK-02170)

Statistical Analysis Plan  
16 August 2019

Zealand Pharma A/S

Clinical Study Report Section 14

Protocol Number: ZP4207-17086

Page 1 of x

14.2.1.5: Sensitivity analysis - time to plasma glucose recovery without censoring for those subjects who require rescue IV glucose before 45 minutes -  
summary table, FAS

→ Repetition of table 14.2.1.1 with different selection of population. Only page 1 output presented here.

Zealand Pharma A/S  
ZP4207-17086 (ZEA-DNK-02170)

Statistical Analysis Plan  
16 August 2019

Zealand Pharma A/S

Clinical Study Report Section 14

Protocol Number: ZP4207-17086

Page 1 of x

14.2.1.6: Sensitivity analysis - time to plasma glucose recovery without censoring for those subjects who require rescue IV glucose before 45 minutes -  
Kaplan Meier survival curve, FAS

→ Repetition of table 14.2.1.2 with different selection of population.

Zealand Pharma A/S  
ZP4207-17086 (ZEA-DNK-02170)

Statistical Analysis Plan  
16 August 2019

Zealand Pharma A/S  
Protocol Number: ZP4207-17086

Clinical Study Report Section 14

Page 1 of x

14.2.1.7: Sensitivity analysis - time to plasma glucose recovery with censoring for those subjects who require rescue IV glucose before 45 minutes -  
summary table, FAS

→ Repetition of table 14.2.1.1 with different selection of population. Only page 1 output presented here.

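### The descriptive Cox model in SAP 11.1 is fitted with ties=discrete but reported as a hazard ratio; where recovery times are tied it estimates a conditional odds ratio

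*SAP*

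**What the plan says.** SAP 11.1 supplements the stratified log-rank test with a Cox model on observed recovery times: "The CPH model will be used for descriptive purposes". A condition for fitting it is that the hazards look "proportional using a graphical comparison of log-minus-log survival curves and no more than two-thirds of the recovery times are censored in each treatment group".

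For ties, the reason given is "the discrete nature of blood sampling in time, and the fact that there must be a true, but unmeasured, ordering of the recovery times". From this the SAP concludes that an exact discrete "partial likelihood for tied failure times will be applied", and it names the PHREG option ties=discrete.

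The result is labelled a hazard ratio throughout: "The treatment group hazard ratios of active versus placebo, will be estimated together with the 95% confidence intervals". Table 14.2.1.1 (Appendix D) has a hazard ratio row, and its footnote 3 reads "Cox proportional hazard model with treatment, age and injection site as fixed effects and baseline plasma glucose as covariate". The homogeneity page of that table uses the same label. Tables 14.2.1.3, 14.2.1.5 and 14.2.1.7 inherit it: "Repetition of table 14.2.1.1 with different selection of population. Only page 1 output presented here".

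The supportive analysis on linearly interpolated times is handled differently: "In this statistical model, `ties=exact` will be used". Its output, Table 14.2.1.10, repeats the layout of Table 14.2.1.1, including the hazard ratio row.

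**The concern.** Three parts of the specification point to a hazard ratio: the label, the log-minus-log check, and the appeal to a true ordering that sampling failed to observe. The option chosen does not estimate one when times are tied. Only the first half of the stated reason, that sampling is discrete, is compatible with ties=discrete.

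Two things follow if ties are common. A reader would take a conditional odds ratio for a hazard ratio in the table that carries the primary result. And Tables 14.2.1.1 and 14.2.1.10 would show two different quantities under one label, so part of any difference between them would come from the tie option rather than from interpolation.

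**Working it through.** **Planning figure.** SAP 5 assumes exponential recovery with medians 10 and 50 min, 20 and 10 patients, 45 min of follow-up and two-sided 5%. Expected recoveries are 20 × (1 − 2^(−45/10)) + 10 × (1 − 2^(−45/50)) = 19.1 + 4.6 = 23.8 (unrounded terms). A Lakatos log-rank calculation gives 90.0%, the stated power. The implied hazard ratio is 50/10 = 5.

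**What each option estimates.** With one recovery per distinct time, both options reduce to the ordinary Cox partial likelihood. With d tied recoveries, ties=discrete compares the observed set with every set of size d from those at risk. That is a conditional logistic likelihood, so exp(beta) is an odds ratio for recovering in that interval. ties=exact sums over the possible orderings of the tied recoveries, so exp(beta) remains a hazard ratio.

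**Direction.** If the placebo cumulative hazard over an interval is h and the hazard ratio is θ, the interval odds ratio is (e^(θh) − 1)/(e^h − 1). For θ > 1 this exceeds θ.

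**Size per interval.** Under the planning assumptions, for an interval of w minutes on the sampling grid (4, 6, 8, 10, 12, 15, 17, 20, 30, 45 min), the odds ratio is (2^(w/10) − 1)/(2^(w/50) − 1):

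| w (min) | Calculation | Odds ratio |
|---|---|---|
| 2 | 0.1487/0.0281 | 5.29 |
| 3 | 0.2311/0.0425 | 5.44 |
| 4 (0–4) | 0.3195/0.0570 | 5.60 |
| 10 (20–30) | 1.0000/0.1487 | 6.73 |
| 15 (30–45) | 1.8284/0.2311 | 7.91 |

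The ratio of log survival, which the log-minus-log check looks at, is 5.0 in every interval.

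**Size of the fitted estimate.** Trials of 20/10/10 patients were simulated with medians 10/10/50 min, using the SAP's three-arm model with age group, injection site and baseline glucose (no covariate effects). Only trials meeting the two-thirds censoring limit were kept, 400 per row. Both likelihoods were fitted to the same data, dasiglucagon versus placebo:

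| Recorded times | Events tied | Median discrete/exact ratio (5th–95th percentile) |
|---|---|---|
| To the second, within protocol windows | 10% | 1.00 (0.99–1.10) |
| To the minute, within protocol windows | 92% | 1.10 (1.03–1.29) |
| Nominal | 96% | 1.14 (1.04–1.45) |

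A separately coded two-arm check without covariates or the censoring limit (1,500 trials) gives 1.13 (1.04–1.38) on nominal times and 1.00 to the second. On nominal times, a placebo median of 75 or 100 min gives 1.18 or 1.17, and 20% of placebo patients rescued at a median of 50 min gives 1.17.

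**Scale.** ln(1.14) = 0.13. Against an SD of the log estimate of about 0.55, that is 0.13/0.55 ≈ 0.24 SD.

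**Which row applies.** SAP 11.1 says actual time points will be used but lists nominal minutes, and later calls these times discrete. SAP Appendix A (Listings) reports seconds only if they were measured. The documents therefore do not settle the resolution.

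**Whether the model is run.** With 10 placebo patients, at most two-thirds censored means at least 4 recoveries by 45 min. The recovery probability is 0.464, 0.340 and 0.268 at placebo medians of 50, 75 and 100 min. The exact binomial probability of meeting the limit is then 0.76, 0.46 and 0.27, or 0.54, 0.28 and 0.15 if 20% of placebo patients are rescued. The log-minus-log check can only lower these figures.

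**The case against.** The strongest reply is that the SAP hides nothing and that little depends on the choice. It calls the model discrete-time, names the likelihood and gives the SAS option, so the estimator is reproducible. The model is descriptive and conditional, and a ties=exact analysis on interpolated times is already planned. All of that stands, and it keeps the point small. It does not make the label right.

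It can also be said that ties may be rare. SAP 11.1 refers to actual times, SAP 11.2 uses actual sampling times for the recovery endpoints, and a ±30-second protocol window up to 20 minutes could hardly be checked with times recorded to the minute. This has force: heavy ties are possible but not established, and 1.14 is the upper of the three base cases, not an expectation.

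Two stronger readings are tempting and are not supported:

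- A reader might infer that the unequal sampling grid alone makes a constant hazard ratio incompatible with a constant odds ratio. It does not. The odds ratio depends on the placebo recovery probability in each interval, not on its width. If the same 46% placebo recovery by 45 min arose from equal conditional probabilities in the ten intervals, a hazard ratio of 5 would give (2^0.45 − 1)/(2^0.09 − 1) = 5.69 in every one. The spread from 5.29 to 7.91 needs exponential recovery, which the SAP assumes for sample size and not for the Cox model.
- A reader might infer from SAP 11.2 that recovery times could be either actual or nominal. Its nominal-time sentence concerns only the change-from-baseline analysis.

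**Conclusion.** The point holds in a limited form. To the extent that recovery times are tied, the quantity labelled a hazard ratio in SAP 11.1 and in Tables 14.2.1.1, 14.2.1.3, 14.2.1.5 and 14.2.1.7 is a conditional odds ratio further from 1. It would then not be the same measure as the one in Table 14.2.1.10.

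The typical inflation runs from nil (times to the second) to about 14% (nominal times) at a true hazard ratio of 5 with exponential recovery. It is small beside the sampling error. Only the paired ratio should be read from the simulations: keeping trials with enough placebo recoveries shifts both estimates, so neither level can be compared with 5.

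A reader might infer that the primary result is at risk. It is not. The confirmatory test is the stratified log-rank test, which does not use this option, and the hierarchy and the 90% power are unchanged. This is a correction worth making because it is cheap, not because a conclusion depends on it.

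**What to change.** In SAP 11.1, specify ties=exact for the Cox model on observed times, including the homogeneity models, and change the words discrete-time and exact discrete to match. Keep the hazard ratio label and the log-minus-log check. This agrees with the ordering argument already given and with the tie option for the interpolated analysis, and it makes no practical difference if times turn out not to be tied. The cost is one SAS option and a few words, with no table shell changes and no new data. It should be done before unblinding, because SAP 6 treats later analyses as post hoc.

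Keeping ties=discrete is possible but costs more. The estimate would have to be relabelled a conditional odds ratio in SAP 11.1 and in Tables 14.2.1.1 (with its homogeneity page), 14.2.1.3, 14.2.1.5 and 14.2.1.7. Table 14.2.1.10 would need its own hazard ratio row label, and the log-minus-log check would have to be replaced by one suited to an odds-ratio model.

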## 5. DETERMINATION OF SAMPLE SIZE

The primary comparison is between the dasiglucagon and placebo treatment arms. From phase 2 results, the median time to an increase of 20 mg/dL of the 0.6 mg dose was approximately 10 minutes. For placebo-treated patients, the median time to recovery is assumed to be more than 50 minutes. Assuming an exponential time-to-recovery distribution with median times of 10 and 50 minutes, a 2-sided log-rank test will be able to detect a difference between dasiglucagon 0.6 mg

and placebo with 90% power with a follow-up time of 45 minutes at a 5% significance level with 20 patients randomized to the dasiglucagon arm and 10 patients to placebo.

GlucaGen® is included as a reference to compare the responses and AE profile to dasiglucagon with those to a marketed product. It is expected that 10 patients in the GlucaGen® group will suffice for the comparison.

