## 10.6 Examination of Subgroups

No subgroup analysis is planned.

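### The Cox homogeneity models for sex, BMI class, ethnicity, race and US/non-US compare nothing between levels, and the planned page will often look discordant when the effect is the same

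*SAP*

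**What the plan says.** - **Aim.** SAP 11.1, after describing the main Cox model, says that "separate CPH models will be calculated to evaluate homogeneity for the following factors" and lists "Sex, BMI class, ethnicity, race, US/non-US". It does not give the terms of these models.
- **Output.** The homogeneity part of the Table 14.2.1.1 shell (SAP Appendix D) has a block for each subgroup level. Each block holds a hazard ratio and a 95% profile interval for dasiglucagon and for GlucaGen, with placebo as reference. No row compares levels, and there is no p-value.
- **Model.** The footnote to that page reads "Cox proportional hazard model with treatment, age and injection site as fixed effects and baseline plasma glucose as covariate". The factor is not in it, nor is its product with treatment.
- **Status.** SAP 11.1 says "The CPH model will be used for descriptive purposes". The Cox model is run only if hazards look proportional and "no more than two-thirds of the recovery times are censored in each treatment group". For ties, "the method using the “exact discrete” partial likelihood for tied failure times will be applied".
- **Subgroups.** SAP 10.6 says "No subgroup analysis is planned", and protocol 10.1.10 says much the same.

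**The concern.** Homogeneity is a statement about the difference in treatment effect between levels. The planned page gives two or more separate effects and leaves the reader to compare them by eye, usually by noting which intervals exclude 1. With 10 placebo children shared between levels, that comparison is dominated by low power and chance, and uneven levels make it worse. The page can therefore suggest that dasiglucagon works in one sex or region and not in another when the true effect is the same.

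The plan is also inconsistent with itself. Treatment hazard ratios by level are a subgroup analysis, which SAP 10.6 says is not planned. A model with only the footnote's terms, fitted to all children, yields a single dasiglucagon hazard ratio, so it cannot fill the shell.

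**Working it through.** **Inputs.** SAP 5: 20 dasiglucagon and 10 placebo children, 45 minutes of follow-up, two-sided 5% log-rank test, 90% power, "Assuming an exponential time-to-recovery distribution with median times of 10 and 50 minutes". The hazard ratio is 50/10 = 5. Sampling times to 45 minutes are from SAP 11.1. The documents do not give the share of children in each level, so it is assumed and varied.

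**1. The plan's own figure.** The Lakatos log-rank calculation uses Z = Σ dᵢ[φᵢθ/(1+φᵢθ) − φᵢ/(1+φᵢ)] / √(Σ dᵢφᵢ/(1+φᵢ)²). Here θ = 5, φᵢ is the ratio of dasiglucagon to placebo children still at risk, and dᵢ is the expected recoveries in each small interval. Φ(Z − 1.96) = 90.0%, so the stated 90% is reproduced. Other formulas give other values (Schoenfeld 95.9%, Freedman 70.8%).

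**2. Information available.**
- Recovery by 45 minutes on dasiglucagon: 1 − 2^(−45/10) = 95.6%.
- Recovery by 45 minutes on placebo: 1 − 2^(−45/50) = 46.4%.
- Expected placebo recoveries: 10 × 0.464 = 4.6, to be shared between the levels of each factor.

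**3. How often the levels disagree when the effect is the same.** 1,000 trials were simulated per setting with the same hazard ratio in both levels. Recovery was read at the sampling times, and the exact discrete partial likelihood was fitted within each level. Significance is by likelihood ratio at 5%, which is the same as a 95% profile interval excluding 1.

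| Share in smaller level (assumed) | One level significant, other not, HR 5 | Same, HR 10 (placebo median 100 min, assumed) | Interaction test rejects, HR 5 |
|---|---|---|---|
| 50% | 45% | 29% | 8.9% |
| 30% | 53% | 35% | 6.0% |
| 20% | 70% | 63% | 4.9% |
| 10% | 88% | 91% | 3.2% |

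Monte Carlo error is about 1.5 points. As a cross-check, a log-rank simulation with 10 v 5 children in each level gives 64% power per level, so exactly one level is significant in 2 × 0.64 × 0.36 = 46%. With 17 v 8 in one level and 3 v 2 in the other, the figure is 85% to 86%.

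The simulation has no covariates and no GlucaGen arm. Its interaction test let each level keep its own baseline hazard. Covariates would be expected to make per-level fits less stable.

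**4. Estimability.** At hazard ratio 5, at least one level has no finite hazard ratio in 34% to 90% of trials over the same range of shares. At an even share, the chance that some level has no placebo recovery is 2 × (1 − 0.5 × 0.464)^10 − 0.536^10 = 0.143 − 0.002 = 14%. That is less than 34%, so a level-only fit can fail even when a placebo child in the level recovers.

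**5. Precision of a direct comparison.** The approximate Wald factor for the 95% interval of the ratio of hazard ratios is exp(1.96 × √Σ(1/expected recoveries)), summed over the four cells.
- 10 v 5 in each level: Σ = 2 × (1/9.56 + 1/2.32) = 1.07, factor 7.6.
- 15 v 8 and 5 v 2: Σ = 1/14.34 + 1/3.71 + 1/4.78 + 1/0.93 = 1.63, factor 12.2.
- 17 v 8 and 3 v 2: Σ = 1/16.25 + 1/3.71 + 1/2.87 + 1/0.93 = 1.76, factor 13.4.

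With under one expected recovery in a cell, the last two are only a rough guide.

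**The case against.** **The output is descriptive and may not appear.** This stands. The Cox model is labelled descriptive, the SAP 10.7 hierarchy does not include it, and the homogeneity page has no p-values. If the censoring condition also covers these models, which SAP 11.1 does not say, the page is dropped when at least 7 of 10 placebo children are censored. At the design placebo rate that has probability Σ(k=7 to 10) C(10,k) 0.536^k 0.464^(10−k) = 24%, before counting censoring for rescue glucose. It rises to 54% or 73% if the placebo median is 75 or 100 minutes (assumed; the SAP says only that it exceeds 50). When the page does appear, the problem remains: given at least 4 placebo recoveries, disagreement is about 52% for the even split and 81% for the most uneven one.

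**The footnote may be a copy.** It repeats the main Cox table's footnote, so an interaction model may have been intended. A reader might infer that the SAP prescribes a separate five-coefficient fit within each level. The documents do not say so; the shell only makes that one possible reading. What is established is that neither text nor shell contains a comparison between levels.

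**An interaction estimate will say little.** True, as the 7.6- to 13.4-fold intervals show. But it states that limit openly, whereas side-by-side intervals hide it.

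**Other stronger readings.** One might say that disagreement mainly reflects level size, but equal levels still disagree in about 45% of trials. One might say that a level without placebo recoveries gives nothing usable, but a profile interval can still give a finite lower bound.

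**SAP 15 announces added supportive analyses.** It does, but that does not reconcile them with SAP 10.6.

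**Conclusion.** The point holds as a should-fix matter of interpretation. As written, the homogeneity analysis does not evaluate homogeneity for any of the five factors. Under the design's own assumptions and one common hazard ratio of 5, the planned page would show one level significant and the other not in roughly 45% to 88% of trials. That rests on exponential recovery, no covariates, a two-level factor and assumed shares of 50% to 10% in the smaller level. On the same data a direct interaction test rejects in 3.2% to 8.9%, close to its nominal 5% with slight inflation at an even split.

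A reader might infer that the primary result or its error control is at risk. The documents do not support that: the primary test is the stratified log-rank test, and these models lie outside the testing hierarchy. What is at stake is any claim of consistent or inconsistent effect by sex, BMI class, ethnicity, race or region.

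**What to change.** In SAP 11.1, for each factor specify one descriptive Cox model on the FAS with treatment, factor, treatment-by-factor, age group, injection site and baseline glucose. Then:

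- For two-level factors, report the dasiglucagon v placebo ratio of hazard ratios between levels with its 95% profile interval.
- For race and BMI class, collapse to two levels stated before unblinding, or report a joint interaction test.
- Show recovered/total by arm for every level of every factor.
- Take per-level hazard ratios from this model only, and only where both arms have at least one recovery in the level. Otherwise mark the hazard ratio and the ratio as not estimable. Do the same if the fit does not converge, since one recovery per arm does not guarantee a finite estimate.
- State whether the proportional-hazards and censoring conditions apply to these models.
- Correct the Table 14.2.1.1 homogeneity shell and footnote, and amend SAP 10.6 to say that these descriptive homogeneity analyses are planned.

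The cost is SAP wording and one shell, with no new data. The drawback is that the intervals will be very wide (about 7.6- to 13.4-fold each way by the approximate formula) and some levels will show counts only.
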